### 8.2 Sample Size Justification

The proposed study is a feasibility study for evaluating the safety and the efficacy of using the Freeze Diamond Polar applicator for treatment of the mons pubis, vaginal introitus and labia anatomical areas and the investigational applicator for treatment of the vagina. Based on previous experience with other RF devices, we believe that the proposed study sample of 10 subjects per each anatomical area (total of 10) will be sufficient to evaluate the safety and the efficacy of the treatment and to obtain qualitative assessments of comfort levels experienced during treatments.

#### 8.3 Study Analysis

• An intermediate safety report based on qualitative analysis of immediate and short term reaction and on AEs will be produced based on analysis of data collected immediately post treatment number one of all the enrolled subjects. This data will be used to adjust further treatments parameter. The interim

Confidential 14

- reports will not affect the continuation of the study. The study will, regardless of the interim report results, be finalized according to this protocol.
- After FU3, the photographs will be sent to independent evaluators that will grade on a GAI scale the change in skin laxity according to photograph of FU3 compare to baseline. Descriptive statistics and correlations between variables will be performed on these results.
- After FU3 the subject assessment on the change in skin laxity on a GAI scale will be analyzed. These results will be correlated with the evaluation done by the independent evaluators in order to learn on the relationships between objective and subjective improvements assessments.
- After FU3 all data collected by response and discomfort/pain level (VAS) and the 5-level short term response scale results will be analyzed using descriptive statistics.
- After FU3, the vaginal pH values will be sent to the PI for formal data entry and analysis. These results will be correlated with the evaluation done by the independent evaluators in order to learn on the relationships between objective and subjective improvements assessments.
- After FU3, the histology slides and molecular assay results will be sent to the PI for formal data entry
  and analysis and archive storage (histology slides). These results will be correlated with the evaluation
  done by the independent evaluators in order to learn on the relationships between objective and
  subjective improvements assessments.

The study reports will provide information for use in research & development, and future planned studies. Descriptive statistics and correlations between variables will be performed.

Safety: Adverse events reported will be listed, documenting course, outcome, severity, and possible relationship to the treatment.

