#### 7.2.2 Skin improvement assessment

The assessment of general improvement in skin appearance will be accomplished by an independent evaluation of photographs.

At baseline and in FU3, a photograph of each of the treated areas will be taken per the photography guidelines. A copy of the images will be sent to independent reviewers. The reviewers will evaluate, for each time point, the improvement in skin appearance in comparison to base line based on the GAI scale (See Appendix B). The results of the evaluation will be recorded in the Photographs assessment log (see appendix

Confidential 10

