## 7.2.4.2 Level of improvement and satisfaction

Subject's Improvement and Satisfaction with treatment will be recorded by using the GAI scale at the last follow up visit (see Appendix B).

Table 1 - Clinical Evaluation Tools

Claim/task	When to conduct?	Tool		
Photography	Baseline, immediately before	Standardized digital photographs		
	treatments 2, 3, FU 3			
Vaginal pH	Baseline, immediately before	Standard pH paper		
	treatments 2, 3, FU 3			
Histopathology & Molecular	Baseline, immediately before	Histology slides, special staining		
Studies	treatments 2, 3, FU 3	and assays.		
Immediate and short term	Immediately following treatments	Examination of skin in the treated		
response evaluation by	1-3	area based on 5 level scale		
investigator		(Appendix F)		
Subject's duration of post-	Before treatments 2, 3, FU 3	Subject Questionnaire on post		
treatment adverse events questionnaire		treatment response (Appendix G)		
Subjects discomfort/pain	Immediately following treatments	VAS (Appendix E)		
assessment	1-3			
Subjects improvement/	FU3.	GAI (see Appendix B)		
satisfaction assessment				
score				
Independent reviewers score	At the end of the study	GAI (see Appendix B)		

Confidential 11

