## 12 Appendixes

## 12.1 Appendix A - Study Flow Chart

## **Study Flow Chart**

	•	\/:a:+ #3	V:-:+ #2	\/:a:+ #4
	V	Visit #2	Visit #3	Visit #4
	Visit #1	4 weeks after	4 weeks after	4 weeks after
Study Activities		Visit #1	Visit #2	Visit #3
·	Screening &Tx1	FU1 and Tx2	FU2 and Tx3	FU3
Qualify for study: Informed Consent, Eligibility assessment, Demographic information, Medical history & treatment related medical examination	Х			
Photographs	Х	х	х	х
PH measurement	х	x	x	x
Histology and Molecular Studies	Х	X	Х	Х
Treatment	Х	Х	Х	
Immediate and short term responses (assessment by investigator)	Х	х	х	
Subject Pain assessment (VAS)	Х	Х	Х	
Subject Duration of Post-Treatment Adverse Events Questionnaire	Х	Х	Х	Х
Subject Treatment Evaluation Questionnaire (v. 4)	Х	Х	Х	Х
Subject's improvement/satisfaction (GAIS)				Х
Concomitant medication	Х	Х	Х	Х
Adverse events recording	Х	Х	Х	Х
Skin improvement assessment by				V
independent evaluators using				X
photographs				

Confidential 21

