## 12.2 Appendix B - GAI Scale

Table 1 - Global Aesthetic Improvement (GAI) scale to be used for both investigator and subject evaluation:

(3)	Very Much Improved
(2)	Much Improved
(1)	Improved
(0)	No Change
(-1)	Worse
(-2)	Much Worse
(-3)	Very Much Worse

Confidential 22

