## 12.3 Appendix C - Photographs Assessment Log

## Independent Evaluators' Form

Subject	ID	Treated Area	Slide Set #	GAI score
(initials)				
		☐Mons Pubis ☐Labia	$\square$ Baseline + $\square$ FU1/ $\square$ FU2/ $\square$ FU3	
		☐Mons Pubis ☐Labia	$\square$ Baseline + $\square$ FU1/ $\square$ FU2/ $\square$ FU3	
		☐Mons Pubis ☐Labia	$\square$ Baseline + $\square$ FU1/ $\square$ FU2/ $\square$ FU3	
		☐Mons Pubis ☐Labia	$\square$ Baseline + $\square$ FU1/ $\square$ FU2/ $\square$ FU3	
		☐Mons Pubis ☐Labia	☐Baseline + ☐FU1/☐ FU2/ ☐FU3	
		☐Mons Pubis ☐Labia	☐Baseline + ☐FU1/☐ FU2/ ☐FU3	
		☐Mons Pubis ☐Labia	☐Baseline + ☐FU1/☐ FU2/ ☐FU3	
		☐Mons Pubis ☐Labia	$\square$ Baseline + $\square$ FU1/ $\square$ FU2/ $\square$ FU3	
		☐ Mons Pubis ☐ Labia	$\square$ Baseline + $\square$ FU1/ $\square$ FU2/ $\square$ FU3	
		☐ Mons Pubis ☐ Labia	$\square$ Baseline + $\square$ FU1/ $\square$ FU2/ $\square$ FU3	
		☐Mons Pubis ☐Labia	$\square$ Baseline + $\square$ FU1/ $\square$ FU2/ $\square$ FU3	
		☐Mons Pubis ☐Labia	$\square$ Baseline + $\square$ FU1/ $\square$ FU2/ $\square$ FU3	
		☐Mons Pubis ☐Labia	$\square$ Baseline + $\square$ FU1/ $\square$ FU2/ $\square$ FU3	
		☐Mons Pubis ☐Labia	$\square$ Baseline + $\square$ FU1/ $\square$ FU2/ $\square$ FU3	
		☐Mons Pubis ☐Labia	$\square$ Baseline + $\square$ FU1/ $\square$ FU2/ $\square$ FU3	
		☐Mons Pubis ☐Labia	$\square$ Baseline + $\square$ FU1/ $\square$ FU2/ $\square$ FU3	
		☐Mons Pubis ☐Labia	$\square$ Baseline + $\square$ FU1/ $\square$ FU2/ $\square$ FU3	
		☐Mons Pubis ☐Labia	☐Baseline + ☐FU1/☐ FU2/ ☐FU3	
		☐Mons Pubis ☐Labia	$\square$ Baseline + $\square$ FU1/ $\square$ FU2/ $\square$ FU3	
		☐Mons Pubis ☐Labia	☐Baseline + ☐FU1/☐ FU2/ ☐FU3	

Confidential 23

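### Section 8.3 names only a correlation between subject and evaluator GAI scores, which cannot quantify a systematic gap between raters; a paired difference with its interval and an agreement table should be added

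*Combined protocol and SAP*

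**What the plan says.** **Scale.** Section 7.2.2 asks the evaluators to judge "the improvement in skin appearance in comparison to base line based on the GAI scale (See Appendix B". Section 7.2.4.2 says: "Subject's Improvement and Satisfaction with treatment will be recorded by using the GAI scale at the last follow up visit", and points to the same appendix. Table 1 sends both ratings to Appendix B. The Appendix B caption calls it a "scale to be used for both investigator and subject evaluation". That names the investigator rather than the independent evaluators, so the shared scale rests on the cross-references in 7.2.2, 7.2.4.2 and Table 1.

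**Unit of rating.** For the evaluators, "a photograph of each of the treated areas will be taken per the photography guidelines", and the Appendix C log ("Independent Evaluators' Form") takes one GAI score per row with mons pubis or labia ticked. Evaluators are plural, but their number is not given. The flow chart has one subject line, "Subject's improvement/satisfaction (GAIS", at FU3, with no area named.

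**Analysis.** For the evaluator grades, section 8.3 states: "Descriptive statistics and correlations between variables will be performed on these results". The subject scores "will be analyzed. These results will be correlated with the evaluation done by the independent evaluators", with the aim of learning how objective and subjective assessments relate. No coefficient, paired difference, agreement measure or rule for combining areas or evaluators is given.

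**Sample size.** The synopsis and section 8.2 give 10 subjects. Sections 2 and 5.1 allow 10 to 300, and dropouts are not replaced.

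**The concern.** When two raters use the same scale, the most direct question about how their ratings relate is whether one scores higher than the other, and by how much. A correlation discards exactly that information. It measures whether the scores rise and fall together, and adding a constant to one rater leaves it unchanged. It also fails in the opposite case: if everyone is rated the same, agreement is perfect and the correlation is undefined.

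This matters because the study has one arm with a baseline comparison, and subjects know that they were treated. A subject GAI well above the evaluators' GAI would change how the subject-reported result is read. A report built on the named analysis could give a high correlation and leave the size of that gap unestimated.

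**Working it through.** There is no planned figure to reproduce: section 8.2 justifies 10 subjects by previous experience, and no alpha, expected correlation or SD is stated. Two-sided 5% and 95% intervals are assumed below, and SDs of the paired difference from 0.5 to 1.5 GAI points are assumed as a range.

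**1. A constant shift.** Take ten made-up evaluator scores: 0 four times, 1 four times, 2 twice. Let each subject score one step higher.
- Pearson r = 1.00 and Spearman = 1.00.
- Means: evaluators 0.8, subjects 1.8, so the mean paired difference is +1.0.
- Exact agreement is 0/10; agreement within one step is 10/10.
- Rated improved (score of 1 or more): 6/10 by evaluators, 10/10 by subjects.
- Concordance coefficient: each variance and the covariance are 5.6/9 = 0.622, so 2 × 0.622 / (0.622 + 0.622 + 1.0²) = 0.55. It registers the gap that r misses.

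**2. Precision of the correlation.** 95% CI = tanh(atanh(r) ± 1.96/√(n − 3)).
- n = 10, r = 0.5: 0.549 ± 1.96/√7 = 0.549 ± 0.741, giving -0.19 to 0.86.
- n = 10, r = 0.3: -0.41 to 0.78. n = 10, r = 0.8: 0.34 to 0.95.
- n = 8 (two dropouts, for illustration), r = 0.5: -0.32 to 0.89.
- n = 300, r = 0.5: 0.41 to 0.58.
- At n = 10 an observed r must exceed 2.306/√(8 + 2.306²) = 0.632 to differ from zero at 5%.

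**3. Precision of the paired difference.** Half-width = t(0.975, n − 1) × SD/√n. At n = 10 this is 2.262/√10 × SD = 0.715 × SD. Power is for a true one-step difference, from the noncentral t distribution.

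| Assumed SD of difference | Half-width, n = 10 | Power for a one-step gap |
|---|---|---|
| 0.5 | 0.36 | above 99% |
| 1.0 | 0.72 | 80% |
| 1.5 | 1.07 | 47% |

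At n = 300 and SD 1.0 the half-width is 0.11.

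So with ten subjects the paired difference is not precise either if the SD is large. It does estimate the gap directly in GAI points, with an interval that shows how much is known.

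**The case against.** Correlation is not all that 8.3 plans. The subject scores are to be analysed before they are correlated, and the section closes by promising descriptive statistics for the study reports. Two distributions on one seven-level scale, set side by side, would reveal a large shift. A reader might infer that the plan leaves over-rating invisible; the text does not support that. What is missing is narrower: a paired estimate with an interval.

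A reader might also infer that one subject score will be matched to several evaluator rows as if they were independent, with too many false positives. Section 8.3 states no unit of analysis, no significance test and no 5% level, so any inflation figure would be hypothetical, and none is used here. Nor is it established that the subject form lacks an area field. The text and flow chart name no area, although the pain VAS is split by area, but no subject GAI form is reproduced.

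The precision point is conditional. It applies to weak or moderate correlations with about ten subjects. It does not apply at r = 0.8 in the same way, nor near 300 subjects.

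Finally, the stated aim is to learn about relationships in a feasibility study, agreement between raters is not an endpoint, and the subject item covers satisfaction as well as improvement while evaluators judge photographs. A difference therefore mixes what is rated with how generously it is rated. This limits the interpretation, and it stands. It does not remove the gain, because 8.3 itself describes both ratings as the change in skin laxity on a GAI scale and sets out to compare them.

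**Conclusion.** The point holds in limited form. The only subject-evaluator comparison that 8.3 names cannot quantify a systematic difference between raters: a uniform one-step gap gives r = 1 with no exact agreement. That is true at any sample size. At 10 subjects the correlation is also imprecise when weak to moderate. The planned descriptive statistics soften the gap but do not close it.

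The conclusion rests on both ratings using the Appendix B scale, which the cross-references support. The sizes given for the paired difference depend on assumed SDs. The primary endpoint, the evaluators' own grading at FU3, is unaffected; what improves is the reading of a secondary, subject-reported result. The change is worth making because it is cheap and serves the plan's own stated aim.

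**What to change.** Amend 8.3 as follows.
- Make the paired subject-minus-evaluator GAI difference, with 95% CI, the main comparison between the two ratings.
- Add a cross-tabulation with the proportions in exact agreement and within one step.
- Define in advance one evaluator value per subject, or per area if the subject GAI is recorded by area, so that n is the number of subjects. If this is a median, state how half-steps are handled in the agreement counts, since two evaluators can produce them.
- Keep a rank correlation with its CI, labelled exploratory.
- State that the difference may reflect satisfaction as well as perceived improvement.

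If area-level subject scores are wanted, settle the area list first: the Appendix C log omits the introitus, which the efficacy objective includes. The field must be on the form before the first FU3 visit, because those ratings cannot be reliably recovered later.

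The cost is a short wording amendment, with the sponsor agreement and IRB approval that section 10.9 requires, a few lines of analysis and at most one form field. The per-subject version needs no new data.

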## 3 Study Objectives

## 3.1 Primary Objectives

- To evaluate the safety of treating the mons pubis, labia and vaginal introitus with the Freeze Diamondpolar applicator.
- To evaluate the safety of the internal treatment of the vagina with the investigational applicator.
- To verify the efficacy of using the Freeze Diamondpolar applicator for improving general skin appearance of the Mons pubis and Labia including improvement of skin irregularities and skin laxity of the female genitalia and introitus.
- To determine and/or quantify any potential regenerative properties associated with the study treatments.

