#### 4 Outcome Measures

## 4.1 Primary Effectiveness Endpoints

• General skin appearance improvement at FU3 compared to baseline as assessed by independent evaluators by photographic assessment, utilizing the GAI Scale.

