## 4.2 Secondary Endpoints

- Subject's assessment of discomfort/pain associated with treatments using a VAS scale, following each of the 3 treatments.
- Subject's satisfaction with the results and assessment of improvement in skin appearance using a GAI scale.
- Subject's vaginal pH with results from pH paper sampling of the vaginal mucosa.
- Subject's histologic and molecular pathology changes with standard molecular histopathology methods.

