## 7.2.3 Histopathology and Molecular Assay documentation

The documentation of histopathologic and molecular assays will be accomplished by use of standard laboratory and pathology methods and commercially available assay kits suitable and designated for research. The results of the documentation (i.e. slide serial and catalogue numbers and assay results) shall be recorded in the Histopathology and Molecular Assay log (see appendix D).

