## 12.4 Appendix D - Histopathology Molecular Assay Assessment log

## Principal Investigator's Form

Subject ID (initials)	Treated Area	Slide Set #	Assay Result
	☐ Mons Pubis ☐ Labia ☐ Introitus	$\square$ Baseline + $\square$ FU1/ $\square$ FU2/ $\square$ FU3	
	☐ Mons Pubis ☐ Labia ☐ Introitus	$\square$ Baseline + $\square$ FU1/ $\square$ FU2/ $\square$ FU3	
	☐ Mons Pubis ☐ Labia ☐ Introitus	$\square$ Baseline + $\square$ FU1/ $\square$ FU2/ $\square$ FU3	
	☐ Mons Pubis ☐ Labia ☐ Introitus	$\square$ Baseline + $\square$ FU1/ $\square$ FU2/ $\square$ FU3	
	☐ Mons Pubis ☐ Labia ☐ Introitus	$\square$ Baseline + $\square$ FU1/ $\square$ FU2/ $\square$ FU3	
	☐ Mons Pubis ☐ Labia ☐ Introitus	$\square$ Baseline + $\square$ FU1/ $\square$ FU2/ $\square$ FU3	
	☐ Mons Pubis ☐ Labia ☐ Introitus	$\square$ Baseline + $\square$ FU1/ $\square$ FU2/ $\square$ FU3	
	☐ Mons Pubis ☐ Labia ☐ Introitus	$\square$ Baseline + $\square$ FU1/ $\square$ FU2/ $\square$ FU3	
	☐ Mons Pubis ☐ Labia ☐ Introitus	$\square$ Baseline + $\square$ FU1/ $\square$ FU2/ $\square$ FU3	
	☐ Mons Pubis ☐ Labia ☐ Introitus	$\square$ Baseline + $\square$ FU1/ $\square$ FU2/ $\square$ FU3	
	☐ Mons Pubis ☐ Labia ☐ Introitus	$\square$ Baseline + $\square$ FU1/ $\square$ FU2/ $\square$ FU3	
	☐ Mons Pubis ☐ Labia ☐ Introitus	$\square$ Baseline + $\square$ FU1/ $\square$ FU2/ $\square$ FU3	
	☐ Mons Pubis ☐ Labia ☐ Introitus	$\square$ Baseline + $\square$ FU1/ $\square$ FU2/ $\square$ FU3	
	☐ Mons Pubis ☐ Labia ☐ Introitus	$\square$ Baseline + $\square$ FU1/ $\square$ FU2/ $\square$ FU3	
	☐ Mons Pubis ☐ Labia ☐ Introitus	$\square$ Baseline + $\square$ FU1/ $\square$ FU2/ $\square$ FU3	
	☐ Mons Pubis ☐ Labia ☐ Introitus	$\square$ Baseline + $\square$ FU1/ $\square$ FU2/ $\square$ FU3	
	☐ Mons Pubis ☐ Labia ☐ Introitus	$\square$ Baseline + $\square$ FU1/ $\square$ FU2/ $\square$ FU3	
	☐ Mons Pubis ☐ Labia ☐ Introitus	$\square$ Baseline + $\square$ FU1/ $\square$ FU2/ $\square$ FU3	
	☐ Mons Pubis ☐ Labia ☐ Introitus	☐Baseline + ☐FU1/☐ FU2/ ☐FU3	
	☐ Mons Pubis ☐ Labia ☐ Introitus	☐ Baseline + ☐ FU1/☐ FU2/ ☐ FU3	

Confidential 24

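### Tissue results go to the PI on a form that shows the visit, and the plan neither names the slide reader nor masks anyone to visit

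*Combined protocol and SAP*

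**What the plan says.** Section 3.1 includes among the primary objectives: "To determine and/or quantify any potential regenerative properties associated with the study treatments". The synopsis lists regenerative properties under both primary and secondary objectives.

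Section 4.1 gives a single primary effectiveness endpoint: "General skin appearance improvement at FU3 compared to baseline as assessed by independent evaluators by photographic assessment, utilizing the GAI Scale". Tissue change appears in Section 4.2 as a secondary endpoint, "Subject's histologic and molecular pathology changes with standard molecular histopathology methods", and again among the secondary objectives in Section 3.2. No endpoint is assigned to the regenerative objective.

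On handling, Section 8.3 says that after FU3 "the histology slides and molecular assay results will be sent to the PI for formal data entry". The same sentence also gives the PI the analysis of these results and the archiving of the slides. Section 7.2.3 relies on routine laboratory and pathology techniques and on "commercially available assay kits suitable and designated for research", and it directs slide identifiers and assay results to the log in Appendix D. That log is titled "Principal Investigator's Form". Each row holds the subject ID (initials), the treated area, a slide-set field with tick boxes for baseline and FU1, FU2 or FU3, and an assay result.

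Section 6.2.3 deletes identifying details from slides and assay results for anonymity. Photographs, by contrast, are graded by independent evaluators (Sections 7.2, 7.2.2 and 8.3).

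**The concern.** The study is single-centre with no concurrent control (Section 2), so every efficacy statement is a comparison of follow-up with baseline. The visit label is therefore the information that lets a reader's expectation move the result. A reader who expects tissue to look better after treatment, and who can see which specimen came after, may grade staining or architecture accordingly.

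The plan recognises the need for distance from the treating side when it sends photographs to independent evaluators. It provides nothing comparable for tissue. The investigator recruits from the investigator's own patients (Section 5.1) and examines the treated area at each treatment session (Section 7.5), so the PI is not a disinterested recipient.

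At stake is how far a favourable histology finding can be trusted as evidence on regeneration. Section 8.3 also correlates the tissue results with the evaluators' photographic grades, to compare objective with subjective assessment. If the tissue reading carries expectation, that correlation is harder to interpret.

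**Working it through.** No formula applies and the plan gives no figure to reproduce on this point, so the check sets the sections side by side.

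1. **Which measure could serve the objective?** The photographic GAI, pain VAS, vaginal pH and questionnaires are not tied to regeneration anywhere. Histology and molecular work (Section 4.2) is the only tissue-level measure. That it serves the Section 3.1 objective is an inference, because the plan makes no link.

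2. **Who enters and analyses?** Section 8.3 names the PI for both, and the title of Appendix D agrees.

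3. **Who reads the slides?** No section says. Section 7.2.3 names no reader, histology score or specific assay. Section 8.3 speaks of assay results being sent, so those values exist before they reach the PI.

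4. **Is the visit hidden at any step?** Appendix D carries the visit boxes and initials. Section 6.2.3 removes identity, which does not conceal the visit. No section mentions coded slides, random reading order, masking to visit, an independent pathologist or a second reader.

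5. **Which results are exposed?** Table 1 lists histology slides, special staining and assays. Slides and staining need judgement. A kit read-out leaves less room for expectation, although the PI still enters and analyses it with the visit in view.

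6. **Is there a practical moment to mask?** Yes. The material goes to the PI only after FU3, when all visits are complete. The interim report in Section 8.3 uses immediate and short-term reactions and adverse events, not tissue, so holding the tissue reading until FU3 withholds nothing the plan needs earlier.

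For workload only: Appendix A sets 4 biopsy time points. With the 10 subjects of Section 8.2, and assuming one site sampled per visit, that is 4 × 10 = 40 specimen sets and 3 × 10 = 30 baseline-to-follow-up comparisons. These are upper counts at n = 10: biopsies may be deferred for infection (Section 5.2.2) and non-completers are not replaced (Section 5.1). They show how many codes are needed. They do not measure bias.

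**The case against.** The strongest reply is that the documents do not show the PI judging anything. Assay results arrive ready-made, Section 7.2.3 points to routine laboratory work, and Appendix D has no column for a histology score. It can fairly be read as a log that ties slide sets to visits. This stands in part. A reader might infer that the treating investigator reads the slides unmasked and so grades the treatment's own effect. The documents do not support that, because the slide reader is never named. What remains is that the reader is unspecified, nobody is masked, and the one described process shows the visit.

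A second reply is that the endpoint is secondary, the hypothesis in Section 8.1 does not mention regeneration, and the analysis is descriptive in a 10-subject feasibility study with no success criterion. All of this is correct. It limits the weight of the point but does not remove it, since the results are meant to inform development and future studies.

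A third reply is that coding leaves larger problems in place. Section 6.2.3 lets specimens come from any treated site, no score or assay is named in advance, and without a control arm a real change over time could not be credited to the device. This too is correct. Coding deals with one source of bias only.

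Finally, visit labels are needed for the analysis. They are not needed at reading or entry, and the change below restores them afterwards.

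**Conclusion.** The point holds as a gap in specification and masking. The plan sends tissue data to the PI for entry and analysis on a visit-labelled form, does not name the slide reader, and masks no one to visit. Judged histology is open to expectation bias, with the likely direction favouring the device. Kit-based assay values are less exposed.

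The size of the bias cannot be derived from the documents. Two stronger conclusions may tempt a reader and are not supported. One is that every specimen is biased: the count of 40 is a total under an assumption of one site per visit, and it mixes kit values with judged slides. The other is that a favourable result would be indistinguishable from reader expectation: nothing in the documents establishes that.

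The conclusion rests on the inference that histologic and molecular change is what would inform the regenerative objective, and on the absence of any masking provision in the documents. It is a worthwhile, inexpensive correction, in proportion to a descriptive feasibility study.

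**What to change.** In Sections 7.2.3 and 8.3:

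- Label every slide and assay sample with a random code that carries no visit, sequence or initials.
- State who reads the slides, and have that person read them in random order after FU3.
- Enter all results by code.
- Have someone other than the PI or the reader hold the key, and link codes to visits only once entry is complete.

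In Appendix D, replace the visit boxes and the initials with the code.

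The cost is a code list, a person at the site to keep it, and one revised form. No extra reader or biopsy is needed. The change does not address the unfixed biopsy site, the absence of a pre-named score or assay, or the lack of a control arm, and the report should state those limits separately.
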